### **6.7.2.4. Duration of Response**

**Duration of Response (DoR):** The DoR time is defined only for responders (patients with a CR or PR). It is measured from the date of first evidence of CR or PR to the date of objective progression or the date of death due to any cause, whichever is earlier. It is calculated as date of progression or death – date of first response evaluation of CR or PR + 1. The DoR will be censored according to the same rules as PFS, with the addition of the following rule: if a patient begins post discontinuation therapy, DoR will be censored on the day of the last response evaluation prior to the initiation of post discontinuation therapy.

A Kaplan-Meier analysis of DoR will be performed to estimate the DoR curve for each arm within each cohort.

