#### ***7.3.2. Discontinuation of Study Drug(s)***

Patients will be discontinued from the study drugs in the following circumstances:

- progressive disease (PD) as defined by RECIST v1.1
- the investigator decides that the patient should be discontinued from study drugs
- the patient or the patient's designee (eg, parents or legal guardian) requests that the patient be withdrawn from study drugs
- the patient is significantly noncompliant with study procedures and/or treatment
- unacceptable toxicity
- the patient has had 2 dose reductions and experiences an AE that would cause a third dose reduction
- the patient, for any reason, requires treatment with another therapeutic agent that has been demonstrated to be effective for treatment of the study indication, discontinuation from study drugs occurs prior to introduction of the new agent
- enrollment in any other clinical trial involving an IP or enrollment in any other type of medical research judged not to be scientifically or medically compatible with this study

If patients discontinue NSAIs/fulvestrant but continue to receive blinded study drug, this will not be considered as discontinuation of study drug.

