**Table JPBQ.10.1. Other Secondary Efficacy Endpoints**

Endpoint	Definition
Overall Survival (OS)	The time from the date of randomization to the date of death from any cause
Objective Response Rate	The proportion of patients with CR or PR according to RECIST v1.1
Disease Control Rate (DCR)	The proportion of patients with CR, PR, or SD according to RECIST v1.1
Duration of Response (DoR)	The time from the date of first evidence of a CR or PR to the date of objective progression or death from any cause, whichever is earlier
Clinical Benefit Rate (CBR)	The proportion of patients with CR, PR, or SD $\geq$ 6 months according to RECIST v1.1

Abbreviations: CR = complete response; PR = partial response; PS = performance status; RECIST = Response Evaluation Criteria in Solid Tumors; SD = stable disease.

**Overall Survival (OS):** OS duration is measured from the date of randomization of any study drug to the date of death from any cause. For each patient who is not known to have died as of the data-inclusion cutoff date for a particular analysis, OS will be censored for that analysis at the date of last contact prior to the data inclusion cutoff date (contacts considered in the determination of last contact date include AE date, lesion assessment date, visit date, and last known alive date).

**Objective Response Rate:** The objective response rate is the percentage of patients with a best response of CR or PR.

**Duration of Response (DoR):** The DoR time is defined only for responders (patients with a CR or PR). It is measured from the date of first evidence of CR or PR to the date of objective progression or the date of death due to any cause, whichever is earlier. If a responder is not known to have died or have objective progression as of the data inclusion cutoff date scores, duration of response will be censored at the last complete objective progression-free disease assessment date.

**Disease Control Rate (DCR):** The DCR is the percentage of patients with a best response of CR, PR, or SD.

**Clinical Benefit Rate (CBR):** The CBR is the percentage of patients with a best response of CR or PR, or SD for at least 6 months.

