**Table JPBQ.6.1. Rules for Determining Date of Progression or Censor for Progression-Free Survival**

Rule	Situation	Date of Progression or Censor	Outcome
1	No baseline tumor assessments	Date of Randomization	Censored
2	No post baseline assessments and no death	Date of Randomization	Censored
3	No documented progression and no death (with a post-baseline tumor assessment)	Date of last adequate tumor assessment	Censored
4	Patient lost to follow-up (or withdrew consent from study participation) before documented progression or death	Date of last adequate tumor assessment	Censored
5	Documented progression	Date of documented progression. If a tumor assessment was done on multiple days, use the earliest date for that visit.	Progressed
6	Death without documented progression	Date of death	Progressed
7	Documented progression or death after missing $\geq 2$ consecutive post-baseline tumor assessments	Date of last adequate tumor assessment before missed assessments or date of randomization, whichever is later	Censored

Note: Progression-free survival and associated outcome is determined by the earliest of the dates above, if more than 1 situation applies.

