### **6.7.3. Sensitivity Analyses**

In order to evaluate the robustness of the primary and key secondary analysis, PFS analysis will also be conducted based on the PP population.

In addition, the following sensitivity analyses will be performed for PFS based on ITT population:

**Progression-Free Survival Sensitivity Analysis 1** (censoring for receiving subsequent systemic anticancer therapy): if a patient is initiated on another anticancer therapy prior to objective progression, including any postdiscontinuation treatment systemic therapy, radiotherapy, or surgical intervention, PFS will be censored at the date of the last complete objective progression-free disease assessment before initiation of the new therapy.

**Progression-Free Survival Sensitivity Analysis 2** (nonobjective progression as a PFS event): if a patient is discontinued from study treatment due to investigator determined non-objective progression (for example, symptomatic deterioration), then the patient's PFS time will be calculated using the date of non-objective progression as the progression date.

**Progression-Free Survival Sensitivity Analysis 3** (forward-dating progressions at unscheduled assessments): if a patient has objective progression at an unscheduled disease assessment, then the PFS time for that patient will be forward-dated to the next scheduled disease assessment.

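### The SAP's added censoring rule for duration of response is not limited to therapy started before progression, so the usual progression can be coded as an event or as censored on the same date

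*SAP*

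**What the plan says.** SAP 6.7.2.4 defines DoR for responders only: "It is measured from the date of first evidence of CR or PR to the date of objective progression or the date of death" from any cause, taking the earlier. It then turns to censoring: "The DoR will be censored according to the same rules as PFS, with the addition of the following rule". The added rule is: "if a patient begins post discontinuation therapy, DoR will be censored on the day of the last response evaluation prior to the initiation" of post-discontinuation therapy.

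The inherited rules are in SAP Table JPBQ.6.1. Rule 5 makes documented progression an event on its own date. The note under the table says: "Progression-free survival and associated outcome is determined by the earliest of the dates above, if more than 1 situation applies".

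Elsewhere the SAP states the ordering condition when it wants one. Rule 4 of the table covers: "Patient lost to follow-up (or withdrew consent from study participation) before documented progression or death". PFS Sensitivity Analysis 1 in SAP 6.7.3 applies "if a patient is initiated on another anticancer therapy prior to objective progression", and it censors at the last progression-free assessment.

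Protocol 10.1.4 has the same endpoint ("It is measured from the date of first evidence of CR or PR to the date of objective progression" or death). It censors only responders who are not known to have progressed or died by the cutoff. It has no censoring for new therapy.

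**The concern.** The trigger in the added rule is the start of any post-discontinuation therapy, whenever it occurs. Protocol 7.3.2 lists "progressive disease (PD) as defined by RECIST v1.1" among the reasons for stopping study drug, so patients commonly start their next therapy after progression, and often because of it. Protocol 10.1.2 no longer requires imaging once objective progression is documented, so the progression scan is normally the last evaluation before the new therapy. Progressive disease is one of the response categories in SAP 6.7.2.3, so that scan counts as a response evaluation.

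Read literally, the rule censors such a patient on the day her response ended. That censoring is informative, because it removes patients at the moment of failure. Two programmers working from the same SAP could produce different DoR curves. If uptake of next therapy differs between arms, the descriptive comparison would be distorted as well. DoR is a listed secondary endpoint in both cohorts.

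**Working it through.** The documents give no DoR event count, median or uptake of next therapy, so there is no stated figure to reproduce. The check has two parts.

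**1. The rules applied to illustrative records.** Partial response at month 4, progression scan at month 14, next therapy at month 15.

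| Record | Rule 5 | Added rule | Earliest-date note |
|---|---|---|---|
| Month-14 scan is the last evaluation | Event at month 14 | Censored at month 14 | Same date, outcome not decided |
| A further evaluation falls between months 14 and 15 | Event at month 14 | Censored after month 14 | Event stands |
| Progression visit runs over several days and the added rule takes a later day | Event on the first day | Censored on a later day | Event stands |

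In the first row DoR is 14 - 4 = 10 months either way. Only the status differs: an event under Protocol 10.1.4, and either an event or censored under the SAP.

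**2. Size if every tie is coded as censored.** Let f be the share of progressing responders who start another therapy before the cutoff. f is not in the documents; the assumed range is 0.3 to 0.9.

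- Share of progression events lost = f: 30%, 50%, 70% and 90% at f = 0.3, 0.5, 0.7 and 0.9.
- With exponential DoR of true median m, the event hazard is ln 2 / m. Keeping a random share (1 - f) of events leaves a hazard of (1 - f) ln 2 / m, so the apparent median is m/(1 - f). For an assumed m of 15 months this is 15/0.7 = 21.4, 15/0.5 = 30, 15/0.3 = 50 and 15/0.1 = 150 months.

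A simulation shows when such a median would be observable. Its inputs are all assumed: 100 responders per arm, exponential DoR, 8-week scans, 10 to 30 months of follow-up after response, and 300 runs per cell. Percentage of runs in which the Kaplan-Meier median is not reached:

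| True median (months) | f = 0 | 0.3 | 0.5 | 0.7 | 0.9 |
|---|---|---|---|---|---|
| 10 | 0 | 0 | 21 | 75 | 99 |
| 15 | 0 | 18 | 66 | 93 | 99 |
| 20 | 6 | 53 | 88 | 97 | 99 |
| 30 | 63 | 93 | 97 | 97 | 99 |

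The f = 0 column is the result when every tie is coded as progressed, or when the rule is limited to therapy begun before progression: no progression event is lost. With a true median of 30 months, the median is often not reached even then, because follow-up is too short. The simulated medians agree with the formula where they can be read (m = 10, f = 0.3: 14.7 against 14.3 months). The number of responders is generous, since the planned arms hold 200 and 100 patients in Cohort A and 100 and 50 in Cohort B. The percentages are illustrations, not forecasts.

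**The case against.** The strongest reply is that the surrounding text already points to an event. The same paragraph ends DoR at objective progression or death, so a patient who progressed before her next therapy has completed her DoR. The new rule is added to the PFS rules and does not replace them, so rule 5 still applies. Where the SAP means to censor a documented progression it says so, as in rule 7 for progression after two or more missed assessments. SAP 6.7.2.3 leaves out responses observed after post-discontinuation therapy begins, and the DoR rule reads naturally as its counterpart. The earliest-date note also keeps the event whenever a later evaluation exists.

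Much of this stands. It shows the probable intent, and it defeats a stronger reading that a reader might take from the rule alone: that it censors every responder who progresses and then starts therapy, removes most DoR events and leaves the medians not reached. The documents do not support that. The result for the usual patient is an unresolved tie, and some patients keep their event. Losing most events would also need f above 0.5, which is not given. The plan has no DoR median or response rate to work from: the 14.4 months in the sample-size section, and the 23.0 months implied by adding 8.6, are PFS medians from randomization.

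What the reply does not do is settle the same-date case. The note selects a date, not an outcome; the added rule says without qualification that DoR will be censored; and the SAP states the missing condition in two other places.

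**Conclusion.** The rule as stated is faulty and should be corrected. For the usual sequence it conflicts with rule 5, with the DoR definition in its own paragraph and with Protocol 10.1.4, and nothing in the SAP says which prevails.

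When therapy begins after the progression date, the size depends on how ties are coded. Coded as progressed, no event is lost. Coded as censored, the loss of progression events equals f (30% to 90% over the assumed range), and the median is inflated by about 1/(1 - f), provided DoR is roughly exponential and starting a next therapy is unrelated to the length of response. Deaths without progression, and progressions not followed by another therapy, remain events under either coding.

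The reach is limited. DoR is estimated by Kaplan-Meier in each arm, with no specified test and no alpha. The primary PFS test and its alpha are unaffected. Progression dates are collected in any case, so an event-based DoR can still be derived.

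**What to change.** Replace the added rule in SAP 6.7.2.4 with wording such as: *For a responder who starts post-discontinuation therapy before objective progression or death, DoR is censored at the last adequate progression-free assessment before that therapy. Objective progression documented before or on the start date of the new therapy is an event, and it takes precedence over censoring on the same date.* Including the start date itself covers therapy begun on the day of the progression scan, where the last evaluation strictly before it would be an earlier scan.

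Then reconcile SAP 6.7.2.4 with Protocol 10.1.4. Even the corrected rule censors some responders whom the protocol would follow to progression. Protocol 12.2.1 allows minor changes of method in the SAP if they are described and justified, and SAP 6.7.2.4 gives no justification. Either state the reason there or align the two texts.

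The cost is a short rewording of the SAP and the matching line in the derivation program. No new data are needed.

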### **6.7.3. Sensitivity Analyses**

In order to evaluate the robustness of the primary and key secondary analysis, PFS analysis will also be conducted based on the PP population.

In addition, the following sensitivity analyses will be performed for PFS based on ITT population:

**Progression-Free Survival Sensitivity Analysis 1** (censoring for receiving subsequent systemic anticancer therapy): if a patient is initiated on another anticancer therapy prior to objective progression, including any postdiscontinuation treatment systemic therapy, radiotherapy, or surgical intervention, PFS will be censored at the date of the last complete objective progression-free disease assessment before initiation of the new therapy.

**Progression-Free Survival Sensitivity Analysis 2** (nonobjective progression as a PFS event): if a patient is discontinued from study treatment due to investigator determined non-objective progression (for example, symptomatic deterioration), then the patient's PFS time will be calculated using the date of non-objective progression as the progression date.

**Progression-Free Survival Sensitivity Analysis 3** (forward-dating progressions at unscheduled assessments): if a patient has objective progression at an unscheduled disease assessment, then the PFS time for that patient will be forward-dated to the next scheduled disease assessment.

## **6.8. Health Outcomes/Quality-of-Life Analyses**

### **6.8.1. Instruments**

Patient-reported outcomes are measured through the following:

- EORTC QLQ-C30: describe target tumor symptom changes
- modified Brief Pain Inventory, Short Form (mBPI-SF): proportion of patients with “worst pain” increase of 2 points or more at any time on-therapy, compared to baseline

### **6.8.2. Quality of Life**

Data from the EORTC QLQ-C30 (Aaronson et al. 1993) instrument will be scored as described by the European Organization for Research and Treatment of Cancer (EORTC) scoring manual (Fayers et al. 2001).

A mixed effects, repeated measures model will be applied to compare treatment arms by cycle with respect to each instrument. The model will include baseline score as a covariate and an unstructured covariance matrix will be utilized. The analysis will include all cycles for which at least 25% of patients in each arm have an assessment.

### **6.8.3. Pain Intensity and Pain Assessment**

Individual pain items on the mBPI-SF (Cleeland 1991) (that is, worst, least, average, and current pain) will be described using descriptive statistics by treatment arm and cycle. A mixed effects, repeated measures model will be applied to compare treatment arms by cycle with respect to

each item. The model will include baseline score as a covariate and an unstructured covariance matrix will be utilized. The analysis will include all cycles for which at least 25% of patients in each arm have an mBPI-SF assessment.

Corresponding analyses will also be conducted for the mean of 7 pain interference with function items. If a patient does not complete Questions 5a through 5g on the BPI-SF, the mean score for the 7 pain interference items will be calculated based on those answered questions when at least 4 out of 7 questions were completed (that is, at least 50% of the questions were answered).

## **6.9. Bioanalytical and Pharmacokinetic/Pharmacodynamic Methods**

Pharmacokinetic (PK) analyses will be performed according to a separate PK analysis plan.

## **6.10. Safety Analyses**

### **6.10.1. Extent of Exposure**

For blinded study drug, extent of exposure will be measured by pill counts and summarized by cycle and cumulatively. The summary will include total dosage taken and dose intensity. Dose intensity will be calculated as the ratio of total dose taken to the assigned cumulative dose. The assigned cumulative dose for each patient during each cycle is 150 mg per dose  $\times$  2 doses per day  $\times$  28 days = 8400 mg. The assigned cumulative dose while on study is 2  $\times$  150 mg  $\times$  number of days on treatment.

For co-administered NSAID, extent of exposure will be measured based on pill count and summarized by cycle and cumulatively. The summary will include total doses taken and dose intensity. Dose intensity will be calculated as the ratio of total doses taken to the assigned number of doses. The assigned number of doses for each patient during each cycle is 1 dose per day  $\times$  28 days = 28 doses. The assigned number of doses while on study is 1 dose per day  $\times$  number of days on treatment.

For fulvestrant, extent of exposure will be measured using the fulvestrant administration eCRF and summarized by cycle and cumulatively. The summary will include total dosage administered and dose intensity. Dose intensity will be calculated as the ratio of total dose administered to the assigned cumulative dose. The assigned cumulative dose for each patient during each cycle is 1000 mg for cycle 1 and 500 mg for cycle 2 and beyond. The assigned cumulative dose while on study is 500 mg + 500 mg  $\times$  number of cycles started.

Dose adjustments and omissions, along with the reason for adjustment or omission, will be summarized for blinded study drug, NSAID and fulvestrant.

### **6.10.2. Adverse Events**

Adverse event (AE) terms and severity grades will be assigned by the investigator using Common Terminology Criteria for Adverse Events (CTCAE) Version 4. In addition, AE verbatim text will also be mapped by the sponsor or designee to corresponding terminology within MedDRA. Adverse events will be reported using the following reporting process:

- The CTCAE Version 4 term reported by the investigator will be mapped to the MedDRA PT and system organ class (SOC) of the corresponding MedDRA lower level term (LLT), unless the reported CTCAE term is 'Other – specify'.
- If the reported CTCAE term is 'Other – specify' the MedDRA LLT, PT and SOC mapped from the verbatim AE term will be used.
- All listings and summaries will use the PT resulting from this process.

Pre-existing conditions are defined as AEs that begin prior to the first dose of study drug.

A treatment emergent adverse event (TEAE) is defined as any AE that begins on or after the day of first dose or any pre-existing condition that increases in CTCAE grade on or after the day of first dose. Comparisons of pre-existing conditions to on-treatment events at the LLT level will be used in the treatment-emergent computation.

A serious adverse event (SAE) is any AE during this study that results in one of the following outcomes:

- death
- initial or prolonged inpatient hospitalization
- a life-threatening experience (that is, immediate risk of dying)
- persistent or significant disability/incapacity
- congenital anomaly/birth defect
- considered significant by the investigator for any other reason.

Important medical events that may not result in death, be life-threatening, or require hospitalization may be considered SAEs when, based on appropriate medical judgment, they may jeopardize the patient and may require medical or surgical intervention to prevent one of the outcomes listed in this definition.

AE will also be classified based on the relationship to the study treatment.

The following TEAE/SAE listings and summaries will be produced:

- Overview of TEAEs
- Summary of TEAEs by PT (all grade and grade  $\geq 3$ )
- Summary of TEAEs by SOC and PT (all grade and grade  $\geq 3$ )
- Summary of TEAEs by PT and maximum grade (1-5)
- List of SAEs
- Summary of SAEs by SOC and PT (all grade and grade  $\geq 3$ ).

The four summaries will be produced for all TEAEs/SAEs and repeated for TEAEs/SAEs related to study treatment.

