#### **10.3.3.3. Venous Thromboembolic Events**

In the randomized Phase 3 studies in breast cancer patients who received abemaciclib in combination with endocrine therapy, there was a greater number of patients who experienced VTEs in the abemaciclib plus endocrine therapy arm than in the placebo plus endocrine therapy arm. The majority of the events were non-serious and were treated with low-molecular-weight heparin. Generally, these events did not result in discontinuation of the study treatment. At this time, the mechanism underlying the association between abemaciclib and the occurrence of VTEs is not known. For suspected or confirmed VTE (eg. deep vein thrombosis or pulmonary embolism), treatment should occur according to usual clinical practice.

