### Overview

Protocol I3Y-CR-JPBQ, A Randomized, Double-Blind, Placebo-Controlled, Phase 3 Study to Compare NSAI (Anastrozole or Letrozole) plus Abemaciclib, a CDK4 and CDK6 Inhibitor, or plus Placebo, and to Compare Fulvestrant plus Abemaciclib or plus Placebo in Postmenopausal Women with Hormone Receptor-Positive, HER2-Negative Locoregionally Recurrent or Metastatic Breast Cancer, has been amended. The new protocol is indicated by amendment (e) and will be used to conduct the study in place of any preceding version of the protocol.

The overall changes and rationale for the changes made to this protocol are as follows:

- Remove the wording of forbid crossover in the continued access period.
- Statistical analysis plan was updated regarding final analysis for Cohort A and Cohort B in different scenarios.
- Incorporated safety monitoring language for hepatic conditions, renal function and VTEs.
- In case of under treatment of another effective therapeutic agent, patients need to be discontinued of study drug instead of discontinuation from study.
- Clarified and updated when study drug need to be suspended or reduced.

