### 3. Revision History

SAP Version 1 was approved prior to unblinding.

SAP Version 2 was approved prior to the first unblinded interim efficacy analysis by the DMC. The overall changes incorporated in Version 2 are summarized as follows:

- Updates to the plan of final analysis of Cohort A and Cohort B in different scenarios.
- Updates to details of analysis plan for baseline disease characteristics and subgroup analyses.
- Other minor editorial changes to add clarity.

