## 6.15. Clinical Trial Registry Analyses

Additional analyses will be performed for the purpose of fulfilling the Clinical Trial Registry (CTR) requirements.

Analyses provided for the CTR requirements include the following:

Summary of adverse events, provided as a dataset which will be converted to an XML file. Both Serious Adverse Events and ‘Other’ Adverse Events are summarized: by treatment group, by MedDRA preferred term.

- An adverse event is considered ‘Serious’ whether or not it is a treatment emergent adverse event (TEAE).
- An adverse event is considered in the ‘Other’ category if it is both a TEAE and is not serious. For each Serious AE and ‘Other’ AE, for each term and treatment group, the following are provided:
  - the number of participants at risk of an event
  - the number of participants who experienced each event term
  - the number of events experienced.
- Consistent with [www.ClinicalTrials.gov](http://www.ClinicalTrials.gov) requirements, ‘Other’ AEs that occur in fewer than 5% of patients/subjects in every treatment group may not be included if a 5% threshold is chosen (5% is the minimum threshold).
- AE reporting is consistent with other document disclosures for example, the CSR, manuscripts, and so forth.

In addition, a participant flow will be created that will describe how many enrolled patients completed the study, and for those who did not, the frequency of each reason for not completing. This analysis will be based on study discontinuation, not treatment discontinuation. A patient will be identified as having completed the study if the patient dies while on the study or the patient had discontinued study treatment and is in follow up at the time of the final analysis. Patients who withdraw consent before the final analysis or who are still on treatment at the time of the final analysis will be identified as not completing the study.

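### The SAP pre-specifies no count of patients with at least one venous thromboembolic event (VTE), although the protocol names VTE as an excess risk of abemaciclib

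*SAP*

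**What the plan says.** Protocol 10.3.3.3 records that in earlier randomized Phase 3 studies "there was a greater number of patients who experienced VTEs in the abemaciclib plus endocrine therapy arm than in the placebo plus endocrine therapy arm". It says that most of these events were non-serious and that the mechanism is not known. Its wording treats VTE as covering more than one diagnosis: "For suspected or confirmed VTE (eg. deep vein thrombosis or pulmonary embolism". The section is recent. The overview in the amendment (e) summary (Protocol Attachment 10) lists among the changes "Incorporated safety monitoring language for hepatic conditions, renal function and VTEs".

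SAP 6.10.2 sets the rule for coding adverse events. The CTCAE term chosen by the investigator is mapped to a MedDRA PT and SOC. If the investigator chose the free-text category, the term mapped from the verbatim text is used instead. The section then says "All listings and summaries will use the PT resulting from this process". The planned outputs are:

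- an overview of treatment-emergent events;
- summaries of these events by PT, by SOC and PT, and by PT and maximum grade;
- a list of serious events;
- a summary of serious events by SOC and PT.

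The summaries are repeated for events related to treatment. Protocol 12.2.12 also works by PT within SOC.

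**The concern.** The protocol describes the known harm as a number of patients per arm who had a VTE. That is a per-patient count over a group of diagnoses. The SAP plans counts for single coded terms and for whole organ classes, and VTE is neither.

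If VTEs are recorded under more than one PT, a reader of the planned tables sees several rows and has to guess how far the patients in them overlap. The trial's result for this harm then cannot be set directly beside the finding that prompted the protocol amendment. A grouping could still be made later. But a term list drawn up after unblinding is open to the criticism that it was chosen with the result in view.

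**Working it through.** No figure in the plan needs reproducing here. The check has two parts: a search of the planned outputs, and a short argument about what PT rows can yield.

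**Step 1. Does any planned output count patients with a VTE?**

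| Place | What is planned | Patients with any VTE? |
|---|---|---|
| SAP 6.10.1 | Exposure, dose intensity, dose adjustments | No |
| SAP 6.10.2 | Overview of treatment-emergent events (contents not specified) | VTE not named |
| SAP 6.10.2 | Summaries by PT, by SOC and PT, by PT and maximum grade; serious events by SOC and PT; list of serious events | Single terms or whole organ classes only |
| SAP 6.10.3 to 6.10.6 | Deaths, laboratory values, vital signs, ECG | No |
| SAP 6.13 | DMC reports: discontinuations, serious events, treatment-emergent events | General summaries; VTE not named |
| SAP 6.14 | Program Safety Analysis Plan, cited for annual report analyses | Not cited for the study's own report |
| SAP 6.15 | Registry output by preferred term | Single terms only |
| Protocol 12.2.12 | Summaries by PT within SOC, some with maximum grade | Single terms or whole organ classes only |

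The SAP does not mention VTE, a grouped or composite term, a MedDRA query, or adverse events of special interest.

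**Step 2. Did the SAP revision pick up the protocol change?** The SAP Version 2 revision history lists the final-analysis scenarios for the two cohorts, "Updates to details of analysis plan for baseline disease characteristics and subgroup analyses", and minor editorial changes. The first item corresponds to a change in amendment (e). No safety item is listed to match the VTE, hepatic and renal additions.

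**Step 3. Can the count be recovered from the PT rows?** Let n1, n2, ..., nk be the numbers of patients in one arm with each VTE term, and N the number with at least one. Then

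max(n1, ..., nk) ≤ N ≤ n1 + ... + nk.

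The lower limit holds when every patient with a rarer term also has the commonest one. The upper limit holds when no patient has two terms.

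The following counts are assumed for illustration and do not come from the documents. Take 200 patients in Arm A1, 6 with deep vein thrombosis and 4 with pulmonary embolism, coded as separate PTs:

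- lower limit: 6, and 6/200 = 3.0%;
- upper limit: 6 + 4 = 10, and 10/200 = 5.0%.

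The PT tables cannot say where in that range the arm lies. The SOC row does not settle it, because it counts patients with any event in the class, whether VTE or not.

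If k = 1, the two limits coincide and the PT row is already the count. The documents do not include the CTCAE-to-PT map, so k cannot be established from them. The two diagnoses named in Protocol 10.3.3.3 make more than one term plausible but do not prove it.

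**The case against.** The strongest reply is that little is lost. SAP 6.1.1 has all analyses done by arm within cohort, so each VTE term will be shown by arm, by maximum grade and at grade 3 or above, and serious cases will also be listed. SAP 6.1 allows further exploratory analyses, and a composite can be derived at any time from the patient-level data. The DMC already receives summaries of serious and treatment-emergent events, with further details left to a DMC Charter that is not part of these documents. If one PT holds nearly all VTEs, the gap almost closes.

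Most of this stands, and it limits the point. It would be wrong to say that VTEs will be invisible or that no arm comparison will be possible. It would also be wrong to say that every safety table is by PT: the overview, the SOC rows, and the exposure, death, laboratory, vital-sign and ECG outputs are not. The reply does not supply a pre-specified count of patients with a VTE. Permission to do an exploratory analysis is not a plan, and it does not fix the list of terms before the data are unblinded.

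A reader might also infer that non-serious VTEs will drop out of the public registry, since SAP 6.15 says that "AEs that occur in fewer than 5% of patients/subjects in every treatment group may not be included if a 5% threshold is chosen". The documents do not support that as a finding. The omission is optional, depends on choosing that threshold, and requires the term to be below it in every treatment group. Serious events are summarised separately.

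**Conclusion.** The point holds in a limited form. The protocol states an excess of patients with VTEs on abemaciclib. The plan, followed as written, produces by-arm counts of individual terms but no pre-specified by-arm count of patients with at least one VTE. That rests on the text alone and needs no assumption.

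The practical consequence does rest on an assumption, namely that VTEs are coded under two or more PTs and that some patients may have more than one. The uncertainty left by the PT tables is then the distance between the largest row and the sum of the rows.

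A numerical estimate of how likely the splitting is to hide an excess would be tempting, but it should not be attempted here. It would need a VTE rate, the number of PTs and the split between them, and the documents give none of these. Nor do they support a claim that the gap matters more because the patients are mainly east Asian.

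This is a worthwhile and inexpensive improvement to the safety reporting. It does not affect the efficacy conclusions.

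**What to change.** In SAP 6.10.2, define a VTE grouped term, either as a standardised MedDRA query or as a list of PTs, and fix it before unblinding. Add one table, by treatment arm within each cohort, giving the number and percentage of safety-population patients with at least one VTE, by maximum grade and by seriousness. Each patient is counted once. The existing PT and SOC tables stay as they are.

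The cost is a few lines of SAP text and one extra table programmed from adverse event data that are already collected and coded. No visit, procedure or clinical rule changes.
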